### **2.2 Study Rationale**

Even with its increasing popularity and use, the impact of ICMs on AF management is still being determined and can even be conflicting. Furthermore, the use of ICM is dependent on physician preference. We hypothesize that dynamic monitoring with ICMs is superior to conventional methods and should be used for all patients with AF. Thus, we aim to measure the outcomes of using ICM versus more traditional approaches in patients with AF.

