## **5 STUDY INTERVENTIONS**

### **5.1 Interventions, Administration, and Duration**

No intervention or administration will be performed due to the observational nature of each phase. Charts of patients enrolled in the study will be reviewed for an initial monitoring method, any changes in

management, including AAD, OAC, CA, as per physicians' preference, arrhythmia recurrence, need for redo CA, and AF-related complication, for 12 months after enrollment. Lastly, the primary outcomes of AF freedom and continued AAD and OAC use will be noted at the end of the study duration.

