## 9.2 Sample Size and Randomization

We will aim for 2500 enrolled participants to result in a 99% power for statistical significance, assuming no difference in AAD, OAC, or CA use rates between those with ICM and non-ICM monitoring methods. We cannot control the exact number of subjects but will attempt a 1:1 allocation into the ICM and non-ICM arms to result in 1250 patients each.

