## 9.4 Data Analyses

Statistical analysis will be performed on both continuous and categorical variables. As appropriate, continuous variables will be reported as mean  $\pm$  standard deviation and compared with two-tailed T-tests and Mann-Whitney testing. Categorical variables will be reported as frequency and percentages and compared with Chi-square testing as appropriate. Cox proportional regression models will be used for hazard ratios and confidence intervals. A p-value  $< 0.05$  will be used to determine statistical significance. Kaplan-Meier graphs will be calculated when appropriate. We will use SPSS [IBM, Armonk, New York] for all statistical analysis.

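### Section 9.4 tests patients as independent although ICM use and most outcomes listed in 9.3 follow physician preference; to the extent both vary by physician, standard errors are too small and the type I error exceeds 0.05

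*Combined protocol and SAP*

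**What the plan says.** **Exposure.** Section 2.2 states that "the use of ICM is dependent on physician preference". The inclusion criteria in section 4.2 likewise leave ICM insertion to the treating physician. Nothing is randomized (4.1.2, 6.2).

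**Outcomes.** Under section 5.1, charts are reviewed for management changes "including AAD, OAC, CA, as per physicians' preference". Section 6.3 leaves visits and changes in management to the treating physician. Section 9.3 lists eight primary outcomes. Six are treatment decisions: timing of AAD, of OAC and of CA, post-ablation changes to AAD and to OAC, and redo ablation. The other two are access to care and arrhythmia recurrence.

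**Analysis.** In section 9.4, continuous variables are "compared with two-tailed T-tests and Mann-Whitney testing". For the rest, "Categorical variables will be reported as frequency and percentages and compared with Chi-square testing as appropriate" and "Cox proportional regression models will be used for hazard ratios and confidence intervals". The threshold is p < 0.05. No section mentions clustering, a centre or physician effect, a mixed model, GEE, frailty, robust variance or a design effect, although section 3 describes a multi-center study.

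**Data and sample size.** Table 1 (section 6.1) lists neither centre nor physician. Section 9.2 makes no allowance for clustering.

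**The concern.** Chi-square, t-tests, Mann-Whitney tests and a Cox model with the usual variance all assume that patients are independent. Two patients of the same physician are not independent if that physician has a habitual way of monitoring AF and a habitual way of treating it. When both habits vary between physicians, part of the difference between arms is a difference between groups of physicians. The effective amount of information then lies closer to the number of physicians than to the number of patients.

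At stake is the only decision rule the plan states. Confidence intervals would be narrower than the data justify, and p < 0.05 would occur under the null more often than one time in twenty. Adjusting for the patient characteristics in Table 1 would not repair this, because the shared physician effect is not a patient characteristic. The six treatment-decision outcomes are the most exposed.

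**Working it through.** **1. The plan's own figure.** Section 9.2 says: "We will aim for 2500 enrolled participants to result in a 99% power for statistical significance". Its stated premise is that treatment use is equal in the two arms. It gives no rate, difference, standard deviation or hazard ratio, so the 99% cannot be reproduced. Under no difference, a two-sided 0.05 test rejects 5% of the time. Working backwards, 1250 per arm gives 99% power for a difference of about 8.5 points from 50%, 8.1 points from 30% or 5.7 points from 10%.

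**2. Inputs.** From the documents: N = 2500, 1:1, alpha 0.05, two-tailed t-tests. Assumed, because the documents give none: k physicians with equal loads m = 2500/k, outcome ICC ρy and ICM-use ICC ρx.

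**3. Formulas.**

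- Variance factor: DE = 1 + (m − 1) × ρx × ρy
- Standard error too small by a factor of √DE
- Actual type I error = 2 × [1 − Φ(1.96/√DE)]

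**4. Middle case: k = 50, m = 50, ρy = 0.05, ρx = 0.3.**

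- DE = 1 + 49 × 0.05 × 0.3 = 1.735
- √DE = 1.32
- 1.96/1.32 ≈ 1.49, so the type I error is 0.137
- Effective N = 2500/1.735 ≈ 1441
- Power for 50% versus 58.5% falls from 99% to about 90%

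**5. Range, with ρy 0.01 to 0.10 and ρx 0.1 to 0.6.**

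| Physicians | Patients each | DE | SE factor | Actual type I error |
|---|---|---|---|---|
| 100 | 25 | 1.02–2.44 | 1.01–1.56 | 0.053–0.21 |
| 50 | 50 | 1.05–3.94 | 1.02–1.98 | 0.056–0.32 |
| 25 | 100 | 1.10–6.94 | 1.05–2.63 | 0.062–0.46 |

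Mild cases are easy to construct. With 25 patients per physician, ρx = 0.2 and ρy = 0.02, the error is 6.1%. With 50 per physician and the same ICCs it is 7.3%.

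**6. Simulation check.** The two-proportion test was simulated under the null with beta-binomial physician effects, 10,000 runs per setting. It gave 0.137 in the middle case, 0.055 at the mildest corner of the grid and 0.450 at the most severe.

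**7. When the problem vanishes.** If ICM use does not vary by physician (ρx = 0), the simulated error is 0.046 to 0.053. If every physician splits patients exactly 50:50, it is 0.039 to 0.055. Both ICM use and outcome must therefore vary by physician for the error to rise.

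**The case against.** **The size is assumed.** This stands. The documents support the direction, since they say both ICM use and management follow physician preference, but not the magnitude. A reader might infer that the false-positive rate is known to be badly inflated, and the documents do not support that. With many physicians and low ICCs it stays near 5%. The opposite extreme is an ICM-use ICC of 1.0, which in the 50-physician case with outcome ICC 0.05 gives DE = 3.45 and about 29%. It requires each physician to use ICM in all patients or in none, and section 9.1, which lets patients cross from traditional monitoring to ICM at any time, fits poorly with that.

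**Not every primary outcome is a physician's decision.** This stands. Sections 1.1, 3 and 5.1 name AF freedom with continued AAD and OAC use as primary. AF freedom, arrhythmia recurrence and access to care are less directly set by the physician. Discretionary visits can still affect whether recurrence is detected.

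**The plan does not rule out a centre term.** Also true. Table 1 is not presented as exhaustive, section 11.2 mentions a site number, and section 9.4 leaves the Cox covariates open. But no such term is planned.

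**Confounding is the larger threat.** A reader might infer that a few physicians who use many ICMs and ablate often are purely a variance problem. That holds only if the two habits coincide by chance. If they are systematically linked, the estimate is biased and robust variance does not cure it. In simulations with no ICM effect, 50 physicians of 50 patients and ICCs of 0.5 (ICM use) and 0.05 (outcome), a cluster-robust test was close to nominal when the habits were unrelated. It rejected about 30% of the time at correlation 0.3 and about 70% at 0.5. The variance fix is necessary but not sufficient.

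**The check covers one test.** The simulation was of a two-proportion comparison. The same reasoning applies to the Cox and rank comparisons, but no figure was computed for them.

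**Conclusion.** The point holds as a conditional one. The plan says that ICM use and AAD, OAC and CA management both follow physician preference, and it then analyses patients as if independent. Whenever both vary by physician, intervals are too narrow and the type I error exceeds 0.05. The excess cannot be determined from the documents. Over the assumed grid the error runs from about 5% to 46%, with about 14% in the middle case. These figures rest on equal physician loads, the stated ICC ranges and physician habits that are uncorrelated with each other. The concern is strongest for the six treatment-decision outcomes in section 9.3 and weaker for access to care, arrhythmia recurrence and AF freedom. It is separate from confounding by physician, and correcting one does not correct the other.

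**What to change.** 1. **Table 1:** add centre and a coded treating-physician identifier. State the attribution rule, for example the physician managing AF at enrollment, because the physician who inserts the device, ablates or prescribes may differ. Assign the code at the site, since section 10.2 sends only de-identified data to the central database.
2. **Section 9.4:** make arm comparisons with GEE or mixed models clustered on physician within centre for binary and continuous outcomes, and with Cox models using cluster-robust variance for times to event. Specify a small-sample correction if physicians are few. Keep the unclustered tests for describing baseline.
3. **Between-physician adjustment:** include centre terms or strata and, where feasible, the physician's ICM-use rate as a covariate or a within-physician comparison.
4. **Section 9.2:** state an effect size and a design effect, so that the power claim can be checked.

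The cost is one or two coded fields per patient, an attribution rule to apply during chart review, and wider confidence intervals. No extra patients or visits are needed for items 1 to 3. If clustering proves negligible, the cluster-aware standard errors will be close to the unclustered ones and little is lost.

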# 10 DATA COLLECTION AND QUALITY ASSURANCE

## 10.1 Data Collection

Data will be collected at each site(s) and recorded in paper or electronic forms.

## 10.2 Data Management

Physical and identifying data will be housed in a locked space at each site. De-identified data will be entered into a secure database at the KCHRRF system, from which they can be analyzed.

## **11 PARTICIPANT RIGHTS AND CONFIDENTIALITY**

### **11.1 Institutional Review Board Review**

This protocol and any subsequent modifications will be reviewed and approved by the IRB or ethics committee responsible for oversight of the study. Study activities should not begin until the document has been approved by the IRB of the investigator's institution or by a central IRB. Patient consent will not be required due to the nature of the study.

### **11.2 Participant Confidentiality**

All reports and communications relating to patients in the study will identify each patient only by an investigative site number, the patient's initials, or the patient's study number. The investigator will maintain a patient identification log containing identifying information for each patient enrolled in the study. This document should contain sufficient information and detail to permit the identification of study patients in case follow-up is required. This information should be treated with strict adherence to professional standards of confidentiality and be kept by the investigator under adequate security and restricted access along with other study records.

### **11.3 Study Discontinuation**

The IRB or principal investigator may discontinue the study at any time as part of their duties to ensure that research participants are protected.

## **12 ETHICAL CONSIDERATIONS**

The study will undergo IRB approval and thus meet all institutional ethical guidelines. All other ethical considerations shall be per the Declaration of Helsinki.

## **13 PUBLICATION OF RESEARCH FINDINGS**

Publication of the results of this trial will be governed by the policies and procedures developed.

